management decisions will be made by the clinical team based on laboratory or bedside monitor-confirmed blood glucose values. The CGMs will be calibrated, at a minimum, every 12 hours with a blood glucose value measured by bedside glucometer. Additional calibrations will be performed if more frequent blood glucose monitoring is deemed necessary by the NICU team. In the “Standard of Care” group, the only change to current management is the potential performance of additional blood glucose checks that may be prompted if repeated unrecognized severe hypoglycemia is detected by the research team. The CGM will remain in place until the infant is no longer being monitored for glycemic stability or until the infant is discharged. If hypoglycemia work-up and management lasts longer than a week, the CGM sensor will be replaced on the seventh day after initial insertion. In the case of a sensor dislodgement or malfunction, it would also be replaced. Lastly, if a patient continues to have unstable hypoglycemia for longer than 28 days (eg. four 7-day cycles of CGM) then their study participation will also end at that time.

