#### ***Description of Study Treatments or Exposures/Predictors***

Continuous Glucose Monitors (CGMs) will be placed in all enrolled patients. CGMs measure glucose concentration in the interstitial fluid of the subcutaneous space every few seconds and report average blood glucose levels approximately every 5 minutes. CGMs have 3 components: a glucose sensor, a transmitter, and a receiver. The glucose sensor is inserted subcutaneously with a 26-gauge introducer needle and remains in place under the surface of the skin for up to 7 days. The sensor’s platinum tip is embedded with glucose oxidase enzyme, which catalyzed a reaction whereby electrical current is generated which is proportional to ambient glucose concentration. The current is then measured and translated into a glucose reading once it is wirelessly sent by the transmitter to the small hand-held receiver. The receiver then displays the glucose level in mg/dL and can alert at specified glucose levels.

*c. Definition of Primary and Secondary Outcomes*

This is a pilot study to determine the feasibility of using CGMs to improve short term outcomes of neonates with hypoglycemia. Planned comparisons for a larger study will be powered from the data obtained. The primary endpoint will be a reduction in incidence and severity of hypoglycemia in infants on the CGM Protocol. Secondary outcomes will include reduction in in time-to-diagnosis, time-to-treatment initiation and time-to-euglycemia on a sustainable feeding regimen.

*d. Data Collection Methods, Assessments and Interventions*

- *Data collection:*

When a subject is first enrolled we will collect demographic Information (age at diagnosis of hypoglycemia, gestational age at birth, sex) as well as physical characteristics (weight and body surface area). Once a subject is on a CGM, the CGM glucose data will be downloaded onto a research team computer and reviewed daily. Laboratory results (including blood glucose levels and critical sample results (ketones, insulin, cortisol, growth hormone, fatty acids, total and free carnitine, plasma amino acids, urine organic acids, lactic acid, pyruvate), brain imaging and EEG readings, all intravenous and enteral sources of glucose, other sources of nutrition, hypoglycemia therapeutic interventions (eg. glucagon, diazoxide, octreotide, corticosteroids and carnitine replacement) as well as underlying etiology of hypoglycemia and other associated diagnoses will be reviewed and collected every 2-3 days.

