- *Assessments:*

The CGM site will be evaluated daily to assess for any signs of bleeding or infection. CGM readings will be downloaded to a study team computer once a day. The CGM data will be reviewed daily to ensure the CGM monitor is functioning properly, being calibrated appropriately and to assess whether any episodes of severe unrecognized hypoglycemia have occurred.

- *Interventions:*

Subjects in the study will have a continuous glucose monitor (CGM) placed in one of their thighs. A numbing cream will be used before the CGM is inserted to reduce pain. The CGM has a small plastic catheter with a needle in it. It comes with an insertion device which pushes the catheter under the skin. The needle is then removed, so only the catheter stays under the skin with the device on top of it. After the CGM is placed, two blood glucose levels will be obtained (usually by heel prick) so that the device can be calibrated. Afterwards at least two blood sugar levels need to be obtained every day so that the CGM can continue to work properly. Infants with hypoglycemia need to have their blood glucose monitored routinely, so on most days no extra blood glucose sampling will be required as we will use the values obtained by the NICU team. Additional blood glucose levels may need to be obtained if the CGM reports current or impending hypoglycemia. All non-CGM monitoring and management decisions will be at the discretion of the NICU team. The CGM may need to be replaced in case of a sensor dislodgement or malfunction, or if it has been in place for more than 7 days. Live CGM glucose values will be available to the medical team in the “CGM protocol” group. Additionally the medical team will be provided print outs of the CGM data on a daily basis for the “CGM protocol” group. CGM data from patients in the “Standard of Care” group will also be reviewed daily. Notification will occur immediately following identification of three unrecognized severe episodes of hypoglycemia. Given that the CGM data will be analyzed daily, this will at most be 24 hours (although most likely less than 24 hours) after the event occurred.

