## 7. Quality Control Method

We will use checklists to verify that every subject has undergone appropriate consent, eligibility screening and safety monitoring during the study. Appropriate CGM placement and function will be performed daily on all enrolled subjects. Glucose data from CGM monitors will be compared to sampled blood glucose levels to assess for accuracy of the CGMs. We will also maintain a log of any protocol deviations and reportable events.

Criteria for early termination of study participation:

- Development of widespread skin disease such that placement of a CGM sensor would be difficult to secure
- Development of infection or colonization with multi-drug resistant organisms (i.e. MRSA, VRE, ESBL producing bacteria)
- Development of significant erythema, induration, infection or other adverse event at the CGM insertion site
- Study cancellation by the sponsor.
- Participant/family failure to follow the study requirements.
- The Principal Investigator judges it is in the best interest for the child to be taken off the study.
- Parent withdraws permission for the child to participate in the study.

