## 8. Data Analysis Plan

Hypoglycemia will be defined as a laboratory or bedside monitor blood glucose value of <50 mg/dL prior to 48 hours of life and <70 mg/dL after 48 hours of life or CGM values below threshold for >30 minutes with no concomitant blood sugar reading. Hypoglycemic episodes within one hour of each other will be considered as one event. Severe hypoglycemia will be defined as less than 40mg/dL. Euglycemia will be defined as 48 hours with blood glucose equal or greater than 70mg/dL after 48 hours of life or equal or greater than 50mg/dL if before 48 hours of life.

We will record all blood glucose levels, laboratory data related to the investigation of the underlying cause of hypoglycemia, intravenous and enteral sources of glucose, and other related therapeutic interventions such as administration of diazoxide, octreotide, glucocorticoids, and carnitine. Data analysis will begin by comparing blood glucose data with information from the CGM monitors to assess for accuracy of the CGMs. This will be done by calculating the mean-absolute-relative-difference (MARD) between sensor-measured glucose levels and laboratory or bedside meter-measured blood glucose values. We will then compare the severity and frequency of hypoglycemia, as well as the time to diagnosis and time to euglycemia on a sustainable feeding regimen between the “CGM Protocol” and “Standard of Care” groups. Chi-squared analysis will be used to assess differences in the incidence of hypoglycemia while the Mann-Whitney U test will be used to analyze differences in time-to-diagnosis and time-to-euglycemia.

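### Section 8 has no rule for invalid sensor readings, so lows from a dislodged or malfunctioning sensor count as primary hypoglycemic events

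*Combined protocol and SAP*

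**What the plan says.** Section 4c defines the outcome: "The primary endpoint will be a reduction in incidence and severity of hypoglycemia in infants on the CGM Protocol". Section 8 lets an event arise from a blood value or, without one, from "CGM values below threshold for >30 minutes with no concomitant blood sugar reading". Episodes within an hour of each other are merged.

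The plan looks at sensor performance in four places:

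- Section 4a, on failed sensors: "In the case of a sensor dislodgement or malfunction, it would also be replaced".
- Section 4d: "The CGM data will be reviewed daily to ensure the CGM monitor is functioning properly, being calibrated appropriately".
- Section 7: "Glucose data from CGM monitors will be compared to sampled blood glucose levels to assess for accuracy of the CGMs".
- Section 8: "Data analysis will begin by comparing blood glucose data with information from the CGM monitors to assess for accuracy of the CGMs", by "calculating the mean-absolute-relative-difference (MARD) between sensor-measured glucose levels and laboratory or bedside meter-measured blood glucose values".

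Section 8 then moves on directly: "We will then compare the severity and frequency of hypoglycemia". It gives no accuracy limit, no rule for readings already recorded by a failed sensor, and no sensitivity analysis.

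**The concern.** A sensor-only event has one safeguard besides its 30-minute duration: no blood value was taken at the time. A sensor that is working loose, or has failed, can meet both conditions. The plan expects such sensors, since it provides for replacing them, but it does not say what happens to what they recorded before replacement.

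Two things are at stake. First, Section 9 says the pilot should supply the variance of the primary outcome for a larger study, and sensor faults scored as events would be part of that variance. Second, the arms differ in how a false low can be caught. In the CGM Protocol arm a reading below 60 mg/dL sounds an alarm and the nurse is asked to check blood glucose. In the Standard of Care arm live readings are hidden, so the same false low usually stands. If staff instead discard doubtful readings case by case, they do so knowing the arm.

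**Working it through.** The only planned figure nearby, 10 infants per arm, rests on pilot convention (Section 9). It cannot be re-derived and is not disputed.

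**1. Does any check reach the event count?** Sections 4a and 4d govern trial conduct: inspect, calibrate, replace. Section 7 compares sensor with blood and stops there. Section 8 calculates MARD and then compares the arms, with no condition linking the two steps. No check removes a recorded reading.

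**2. MARD does not show direction.** Suppose true glucose is 80 mg/dL. A sensor always 15% low reads 80 × 0.85 = 68. One alternating 15% low and 15% high reads 68 and 92. Both have MARD 15%, but mean bias is −15% and 0%. All readings of the first sensor fall below 70, against half of the second's.

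**3. How much bias makes a false low?** A sensor reading a fraction b low shows the threshold when true glucose is threshold/(1 − b). The values of b are assumed.

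| b | reads 70 at true | reads 60 at true |
|---|---|---|
| 5% | 73.7 | 63.2 |
| 10% | 77.8 | 66.7 |
| 15% | 82.4 | 70.6 |
| 20% | 87.5 | 75.0 |

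**4. Upper bound for one failed sensor.** Section 4a requires calibration at least every 12 hours. Separate events need lows of just over 0.5 h and gaps of just over 1 h. Eight lows and seven gaps take about 8 × 0.5 + 7 × 1 = 11 h; a ninth would need about 12.5 h. So at most 8 false events fit between two calibrations.

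**5. Gradual drift (simulated; all inputs assumed except the 5-minute readings, the 70 mg/dL threshold, the 30-minute rule and the 12-hour maximum).** True glucose had mean 80, 85 or 90, SD 6, floor 72 and autocorrelation 0.95 between readings. Drift was linear from zero at calibration, with SD 10, 15 or 20 mg/dL at 12 h and the same slope for shorter gaps. Reading noise had SD 3. A false event was at least 7 consecutive readings below 70. There were 20,000 intervals per setting.

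| Calibration gap | Intervals with a false event | Per infant-week | Intervals with such a run below 60 | Below 40 |
|---|---|---|---|---|
| 12 h | 3.9% to 33.0% | 0.5 to 4.6 | 0.3% to 15.3% | 0% to 1.7% |
| 6 h | 0.1% to 14.8% | 0.04 to 4.2 | 0% to 1.7% | 0% |
| 4 h | 0.03% to 6.1% | 0.01 to 2.6 | 0% to 0.1% | 0% |

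The weekly figure is the share times 14, 28 or 42 intervals, counting at most one event per interval. Part of the fall in share at shorter gaps reflects shorter intervals: per week, the worst setting falls only from 4.6 to 4.2 between 12 h and 6 h.

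**6. What a one-sided excess would do.** Let true incidence be p in both arms, and let a share q of otherwise event-free Standard of Care infants have a false event. Observed incidence there is p + (1 − p)q. Exact chi-squared rejection at 10 per arm, nominal 5%, without continuity correction (p and q assumed):

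| p | q = 0 | q = 10% | q = 30% | q = 50% |
|---|---|---|---|---|
| 30% | 3.7% | 4.8% (7 points) | 13.7% (21) | 32.7% (35) |
| 50% | 4.2% | 4.7% (5 points) | 8.8% (15) | 18.2% (25) |
| 70% | 3.7% | 3.9% (3 points) | 5.4% (9) | 9.0% (15) |

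Brackets give the spurious difference. With continuity correction the p = 50% row becomes 1.3%, 1.5%, 3.4% and 8.6%.

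**The case against.** Sensor performance is used in conduct: function is reviewed daily, failed sensors are replaced and blood values recalibrate the device. The 30-minute rule screens out brief noise. Twelve hours is the longest permitted calibration gap, and Section 4d expects blood glucose to be monitored routinely in these infants. The trial is an unpowered pilot that, by Section 1, is meant to test its outcome measures, so learning sensor accuracy before fixing a cutoff is defensible. All of this stands, and it limits the size of the problem. It does not supply the missing rule for recorded data.

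Several stronger readings are tempting but unsupported:

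- **Contradicting blood values are ignored.** A blood value at the time of the low removes the sensor-only route. Only pairs taken at other times have no effect.
- **A later disagreeing pair proves the low false.** Suppose a sensor calibrated at 20:00 reads 72 against blood 95 at 08:00, an error of −23. Under linear drift the error at 01:00 is −23 × 5/12 = −9.6, so a reading of 60 then implies true glucose of 69.6, a real low.
- **False severe events are material.** In the simulation, runs below 40 occur in at most about 1.7% of intervals.
- **The error only dilutes the difference.** Below 60 mg/dL it can instead exaggerate a CGM benefit.
- **Blood agreement should be the primary condition.** In the 12-hour model, dropping intervals whose closing pair differs by more than 20% removes about 30% to 89% of false events, but only 4% to 68% at 6 h and 0% to 33% at 4 h. With an assumed mean of 70 to 80, SD 10 and no floor, it also drops 12% to 45% of 12-hour intervals with a correctly flagged true low. It could act unequally, because alarms give the CGM arm more blood pairs.

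**Conclusion.** The gap is real and should be closed. As written, Section 8 scores lows from a dislodged or malfunctioning sensor as primary events, and the accuracy step cannot change that. The direction of the asymmetry below 60 mg/dL follows from the alarm and masking rules in Section 4a. Between 60 and 69 mg/dL after 48 hours, false lows can go unchecked in both arms unless a trend or rate-of-fall alarm prompts a check, so there the effect is mainly noise.

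The size is not established. The documents give no sensor failure rate, accuracy or drift. The 4% to 33% is the result at the longest allowed calibration gap under assumed drift, and it describes a drifting sensor rather than a failed one. The rejection rates assume that false events occur in one arm only. For an unpowered pilot of 10 per arm, the main harm is to the event rates and variance passed on to the larger trial, with possible bias in the comparison as the second.

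**What to change.** Add to Section 8:

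1. Readings from a sensor found dislodged or malfunctioning are invalid from its last agreeing blood pair until replacement. They leave both the event count and the monitored hours. A program applies the rule from the sensor log, without the arm label, and excluded hours are reported by arm.
2. Signed sensor bias is reported beside MARD.
3. Two sensitivity analyses count (a) blood-confirmed events only and (b) sensor-only events whose bracketing blood pairs agree with the sensor. One agreement margin, fixed in advance, serves items 1 and 3. A percentage and an absolute margin are not interchangeable: at 60 mg/dL, 20% is 12 mg/dL, not 20.

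Agreement between pairs should stay out of the primary rule for sensors not found to have failed, for the reasons given above. Item 1 therefore deals with failed sensors, while items 2 and 3 show how far drift matters.

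The cost is a few lines of text and some programming on data already collected, with no change to care. Some sensor hours and some true lows will be set aside. Fewer blood pairs in the masked arm may lengthen its invalid periods, which is why excluded hours must be shown by arm.

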**a) Reduce the number and severity of hypoglycemic events**

*Hypothesis: Use of CGMs will provide real-time blood glucose trends, allowing hypoglycemia to be predicted and prevented, or detected and treated before becoming severe or symptomatic.*

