**2. Background and Significance**

Neonatal hypoglycemia affects approximately 10% of all newborns, and up to 50% of infants with risk factors such as maternal diabetes, small for gestational age (SGA; <2500g), large for gestational age

(>4000g), birth at <37 weeks gestational age, and maternal beta blocker or terbutaline therapy 48 hours prior to delivery (1,2). Timely detection and treatment of neonatal hypoglycemia are critical, as failure to do so is associated with poor long-term neurodevelopmental outcomes (3,4). Neonates with symptomatic hypoglycemia are at risk for learning disabilities, seizure disorders, mental retardation and cerebral palsy (5). SGA infants with recurrent hypoglycemia, for example, have been reported to have smaller head circumference at 18 months and lower scores on psychometric tests at 5 years (4). Infants of diabetic mothers with resultant neonatal hypoglycemia have been found to have higher incidence of attention deficits, motor control dysfunction and perception deficiencies (6). Persistent hypoglycemia, often associated with serious metabolic conditions such as hyperinsulinism and fatty acid oxidation defects, is also associated with worse neurological outcomes (7).

Part of the challenge in managing neonatal hypoglycemia is that signs and symptoms can be nonspecific or absent. Clinical signs of hypoglycemia include irritability, poor feeding, tremulousness, and somnolence, all of which can be subtle or mistaken for normal neonatal behavior. The more severe signs, such as seizure, hypothermia, respiratory depression, and coma usually do not present until hypoglycemia has been severe or prolonged (5).

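### Section 8 counts hypoglycemic events without regard to their length, so in infants with relapsing lows the event count can move opposite to the time spent low

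*Combined protocol and SAP*

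**What the plan says.** Section 8 gives two routes to an episode. The first is a single low blood value: "Hypoglycemia will be defined as a laboratory or bedside monitor blood glucose value of <50 mg/dL prior to 48 hours of life and <70 mg/dL" (the higher cut applies once an infant is more than two days old). The second is "CGM values below threshold for >30 minutes with no concomitant blood sugar reading". Episodes are then merged: "Hypoglycemic episodes within one hour of each other will be considered as one event". On depth, "Severe hypoglycemia will be defined as less than 40mg/dL".

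The count matters because aim (a) in Section 1 is to "Reduce the number and severity of hypoglycemic events", and Section 4c states that "The primary endpoint will be a reduction in incidence and severity of hypoglycemia in infants on the CGM Protocol". Section 9 expects ten infants per arm to yield the variance of frequency and severity for a later, larger study.

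The hypothesis under aim (a) is that CGM works by "allowing hypoglycemia to be predicted and prevented, or detected and treated before becoming severe or symptomatic". Section 2 says that the more serious clinical signs "usually do not present until hypoglycemia has been severe or prolonged".

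No outcome in the plan is time below threshold, area below threshold or episode length. The 30 minutes in Section 8 is a condition for a CGM-only low to count at all; it does not measure length once the low has counted.

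**The concern.** One way CGM could help is by bringing a low to notice sooner, so that it is treated sooner and lasts less long. A count that ignores length, combined with a depth cut at 40 mg/dL, cannot register that shortening. In an infant whose glucose falls again after recovery, the count can even go the wrong way: a long unnoticed low is one event, whereas several short, treated lows more than an hour apart are several events.

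At stake is how a small pilot is read. Section 1 says the results will be used to judge whether the outcome measures are valid and to inform power and sample size. If the only frequency measure can rise while exposure falls, a difference in counts between arms is hard to interpret, and so is a variance taken from those counts.

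**Working it through.** **No plan figure to reproduce.** Section 9 gives ten per arm by convention and says the study is not powered. The check is to apply the Section 8 rule literally to constructed glucose traces.

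**Inputs from the documents.** Threshold 70 mg/dL after 48 hours of life; a blood value below threshold counts at any length; a CGM-only low counts if it exceeds 30 minutes; episodes within 60 minutes merge; severe is below 40 mg/dL (all Section 8). CGM readings arrive about every 5 minutes (Sections 2 and 4).

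**Assumptions.** The trace shapes are invented for illustration: an infant older than 48 hours, lows at 55 mg/dL, otherwise 85 mg/dL. Area below threshold = (70 − 55) × minutes low = 15 × minutes low.

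**Step 1: an 8-hour window, CGM runs only.**
- Unbroken low: 480 minutes, 1 event.
- Three 40-minute lows more than 60 minutes apart: 3 × 40 = 120 minutes. Each exceeds 30 minutes and none merge, so 3 events.
- Time low: 120/480 = 25%, a 75% fall. Count: 3/1, a threefold rise.
- At 55 mg/dL no reading is below 40, so neither pattern contains severe hypoglycemia.

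**Step 2: other patterns on a 24-hour trace.**

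| Pattern | Minutes low | Area (mg/dL × min) | Events |
|---|---|---|---|
| One 6-hour low, no blood value | 360 | 5400 | 1 |
| Three 40-minute lows, 80-minute gaps, CGM only | 120 | 1800 | 3 |
| Four 20-minute lows, 80-minute gaps, each blood-tested | 80 | 1200 | 4 |
| The same four lows, none blood-tested | 80 | 1200 | 0 |
| Six 20-minute lows, 40-minute gaps, each blood-tested | 120 | 1800 | 1 |

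Minutes and area rank the 6-hour low as the worst. The count ranks it below the second and third patterns and level with the last.

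**Step 3: range within 6 hours.** For lows of d minutes with 65-minute gaps, the most events that fit is 1 + floor((360 − d)/(d + 65)).
- d = 10: 5 events, 50 minutes low.
- d = 20: 5 events, 100 minutes.
- d = 30: 4 events, 120 minutes.
- d = 40: 4 events, 160 minutes.

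Against 1 event and 360 minutes, the count is 4 to 5 times as high while time low falls by between 1 − 160/360 = 56% and 1 − 50/360 = 86%. Lows of 30 minutes or less count only if blood-confirmed.

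**Step 4: a shorter window.** Section 2 cites detection by CGM up to 3 hours before the scheduled test. One 180-minute low is 1 event; two 40-minute lows 100 minutes apart are 2 events and 80 minutes, a fall of 1 − 80/180 = 56%.

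**Step 5: where the result depends on the reading.** Give the 6-hour low three blood values, at the start and 180 and 355 minutes later. If the CGM run joins them, it is still 1 event. If only blood values define episodes, they are 180 and 175 minutes apart and score 3 events. Section 8 does not say which applies.

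**The case against.** The best reply is that a single event for a long low is one reading, not the stated rule. Section 8 uses CGM runs where there is no concomitant blood reading, and never says that a run links separate blood values. Infants with hypoglycemia are sampled routinely (Section 4d). Under a blood-only reading with draws about 3 hours apart, the 6-hour low scores 3 events, the same as three short lows, and the contrast disappears. This stands as a limit: the example holds where a CGM run defines the episode. It also shows that the end of an event needs defining.

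A reader might go further than the documents allow in four ways.

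- **That the count will worsen under CGM.** The traces show only that it can. It needs repeated relapse more than an hour apart without offsetting prevention, and the documents give no frequency for either. Prevention is part of the stated hypothesis and would lower the count.
- **That the planned test is distorted.** If the chi-squared test for incidence counts infants with at least one event, splitting one low into several changes nothing. The unit is not stated.
- **That the outcome misses the objective.** Aim (a) is literally the number and severity of events, and stopping a fall before 40 mg/dL would register as less severe hypoglycemia. Shortening of episodes is an inference from the mechanism.
- **That the effect has nothing to do with blood sampling.** The three-low pattern needs no blood values, but in practice alarms prompt checks in the CGM Protocol arm only. The same four 20-minute lows score 4 when tested and 0 when not.

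It can also be said that time-to-treatment and time-to-euglycemia pick up part of the benefit, and that a pilot which keeps the traces can compute burden afterwards. Both are fair. Neither secondary outcome measures time spent low, however, and a burden measure chosen after the data are seen is weaker evidence than one named in advance.

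**Conclusion.** The concern holds in limited form. The Section 8 count has no length weight and no stated event end, and severe hypoglycemia is defined by depth only. Where a CGM run defines the episode, the count can rise while exposure falls: from 1 to 3 events as time low drops 75% over 8 hours, and to as many as 4 to 5 events as it drops 56% to 86% in the 6-hour scenarios.

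This rests on constructed traces, on lows more than an hour apart, and on sensor data continuous enough to join the long low. It bears on event number and frequency and on the variance that Section 9 would carry forward. It does not establish a bias in the incidence test, a worse result for the CGM Protocol arm, or a failure of the outcome to address aim (a). It is worth correcting before analysis because the remedy is cheap.

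**What to change.** In Section 8:

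- Add one pre-named burden measure per infant: percent of valid sensor time below the age-specific threshold. Compute it identically in both arms and compare it with the Mann-Whitney test, which the plan already uses for its time outcomes. Report percent of valid sensor time below 40 mg/dL as the severity companion.
- Keep the event count beside it, and report episode duration with the count.
- State when an event ends, and whether a CGM run joins blood values that fall within it.

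In Section 9, estimate the variance of the burden measure as well as that of the event count.

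Naming the unit of the chi-squared test would also settle how far this point reaches into the incidence comparison.

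The cost is analysis wording and some programming. Every infant wears the sensor, readings arrive about every 5 minutes, and data are downloaded daily in both arms. The downside is that burden inherits sensor error and gaps in wear. Calibration frequency may also differ by arm, since Section 4a adds calibrations when blood monitoring is more frequent and alarms prompt extra checks in one arm. The MARD that Section 8 already plans, and valid wear time, should therefore be reported by arm.
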